Study Protocol and Statistical Analysis Plan

Identifiers: NCT02723916

Title: Parent Training in Pediatric Care: A Self Directed Tablet-Based Approach

Date of Document: September 1, 2015

The **specific aims** are:

Aim 1. Test the direct effects of the 6-module eCPP on parenting outcomes (parenting behavior, self-efficacy, and stress) and child outcomes (child problem and prosocial behavior) compared to an enhanced usual care control condition among low-income parents with young children seen in primary care.

HYPOTHESIS 1A: Relative to parents in the control condition, parents in the eCPP condition will report greater improvements in parenting and child outcomes at the 3-month assessment.

HYPOTHESIS 1B: The improvements in parenting outcomes and child outcomes the eCPP condition relative to the control condition will be maintained through the 6- and 12-month assessments.

Aim 2. Compare the cost-effectiveness of the eCPP relative to control for parenting and child outcomes.

HYPOTHESIS 2: The eCPP is cost-effective relative to control for parenting and child outcomes.

Aim 3. Quantify the levels of program implementation of the eCPP in primary care using the RE-AIM

framework. **RESEARCH QUESTION 3:** What is the degree of Reach, Efficacy, Adoption, Implementation, and Maintenance of the eCPP intervention in pediatric primary care

Study Design. The study will be a person-randomized clinical trial comparing the effects of the eCPP tablet-based intervention to an enhanced usual care control condition (Table 1). Parents ($n = 312$) of 2- to 5-year-old children will be recruited from 4 primary care practices and randomly assigned to either the eCPP or control condition. Randomization will occur within sites at the participant level. Intervention parents ($n = 156$) will complete the 6 modules of the eCPP over a period of 3 months (~2 weeks/module; intervention phase) with ongoing access to the program (reference phase) throughout the remainder of the study period. Control condition parents ($n = 156$) will receive tablet-based parenting materials that they would normally receive at their primary care practice (e.g., information regarding nutrition, immunization, and exercise) and have access to the materials over the same intervention time period. Data collection in both conditions will occur at baseline and at 3, 6, and 12 months post-baseline. A descriptive design will be used to evaluate implementation of the eCPP from the perspective of practice sites, clinicians, and parents. Guided by the RE-AIM framework, we will use surveys, electronic health records, data usage metrics, and post-implementation assessments to evaluate the implementation process over the study period.

Measures.

Aim 1: Randomized Control Trial. All measures are written at the 5th grade reading level and administered on an Android tablet as computer assisted, self-interviews (CASIs). An audio option (audio-CASI) is available if parents prefer to listen to the questions. All control and outcome data are obtained by parent self-report and will be collected at each of the 4 data collection time points (baseline, 3, 6, and 12 months post baseline). Previous findings from RCTs of the group-based CPP have found significant findings across three sources of data: parent self-report, teacher report and parent-child observation.^{14,24} In these studies, the parent self-report findings have consistently agreed with other methods of measuring parent and child outcomes. For this reason, the source of parenting and child outcome data for this study will be parent self-report alone.

Control variables. We will collect information on social determinants of health that may affect parenting and child behavior outcomes. The social determinants of health are: general demographics, income and economic hardship, and neighborhood and community characteristics.⁶⁹ Demographics (e.g., age, race/ethnicity, household structure) will be collected using a 21-item demographic inventory. Income and economic hardship will be assessed with a 9-item income inventory and an economic hardship scale (7 items).⁷⁰ In our current study, Cronbach's alpha for the economic hardship scale was .68. Neighborhood and community characteristics will be collected using 9 items from the National Survey of Children's Health.⁷¹ Questions include perceived neighborhood social support, condition, and safety.

Outcome variables. Primary parenting outcome variables include parenting behavior, self-efficacy, and stress. The primary child outcomes are child behavior problems and prosocial behavior. All survey data are obtained by parent self-report and will be collected at each of the 4 data collection time points (baseline, 3, 6, and 12 months post baseline). Parenting behavior will include parenting discipline strategies and positive parenting

behavior. Parenting discipline strategies will be measured using the 40-item Parent Questionnaire (PQ). Three scales – warmth, follow-through on discipline, and corporal punishment – using a 5-point scale measure how parents discipline their children. Cronbach's alpha for the three subscales are .84, .80, and .68, respectively.¹⁴ The PQ is a valid measure of parenting behavior and discipline skills in African American and Latino families.^{14,72} Positive parenting behavior will be assessed using the 21-item Parenting Young Children (PARYC) measure using a 7-point scale. There are three subscales for the PARYC: supporting positive behavior, setting limits, and proactive parenting. Cronbach's alpha for the three scales are .78, .79, and .85, respectively.⁷³ Parenting self-efficacy will be evaluated using the 17-item Parenting Sense of Competence Scale (PSOC). The PSOC has two subscales using 6-point scales: satisfaction (person's liking of the parenting role) and efficacy (person's perceived competence in the parenting role). Cronbach's alpha for the total scale, satisfaction, and efficacy subscales are .79, .80, and .80, respectively.^{74,75} The PSOC is correlated with other measures of family life and child behavior, and the satisfaction subscale is strongly correlated with measures of child behavior, parent well-being, and parenting style.^{74,76} Parenting stress will be assessed with the Parenting Stress Index-Short Form (PSI-SF). The PSI-SF is a 36-item survey with three scales using a 5-point scale: parental distress, parent-child dysfunction, difficult child.⁷⁷ Cronbach's alpha is .90 for the total scale, .79 for parental distress, .80 for parent-child dysfunction, and .78 for difficult child.⁷⁸ The PSI-SF is a valid measure of parenting stress in multicultural samples and for parents from lower socioeconomic groups.^{79,80}

We will measure child behavior problems using the Eyberg Child Behavior Inventory (ECBI).⁸¹ The ECBI is a 36-item scale designed to measure the presence and intensity of problem behavior. Each item is measured on two scales: the Problem Scale (dichotomous) and Intensity Scale (7-point). The ECBI is a valid measure of child behavior problems, with established convergent validity across racial and ethnic populations and economically and linguistically diverse samples.⁸¹⁻⁸³ Cronbach's alpha reliabilities of the Intensity and Problem Scale scores are .92 and .99.²⁴ In addition, the Strengths and Difficulties Questionnaire (SDQ) will provide a measure of child behavior problems and prosocial behavior. The 25-item SDQ has a five-factor structure (emotional, conduct, hyperactivity-inattention, peer, and prosocial) using a 3-point scale. Mean Cronbach's alpha for the SDQ is .73.⁸⁴ The SDQ has been validated in multiple cultures and socioeconomic levels.⁸⁵

Aim 2: Cost effectiveness analysis. Data for the cost effectiveness analyses will be drawn from invoices, staff report, study records, EHR, and eCPP electronic time stamps (Table 4). Resources used for the

Table 4. Description of Resource and Cost Measures

Cost Category	Source	Unit of Measure	Translation to Costs
eCPP costs			
eCPP delivery costs	Invoice	Participant	Average cost/participant
Orientation delivery costs			
EHR modification	Programmer report	Minutes/site	Programmer average hourly wage
Clinician time receiving study orientation	Study records	# of clinicians Minutes/clinician	Clinician average hourly wage
Time to lead orientation	Study records	Minutes	Study staff average hourly wage
Clinician costs			
Time to introduce study*	EHR	Minutes/ participant	Clinician average hourly wage
Parent costs			
Time spent learning about the study*	EHR	Minutes/ participant	Parent average hourly wage
Time spent completing eCPP modules	digital time logs	Minutes/ participant	Participant average hourly wage

EHR = Electronic Health Record; *time for introducing and learning about the study includes all parents (non-participants and participants), averaged across the # of participants.

intervention include the eCPP costs (e.g., tablet, tech support, and maintenance costs), modification of the EHR, orientation for clinicians, and time for the clinician to introduce the study to parents during well-child visits. Participant costs are primarily the parents' opportunity costs, representing the value of their time spent in the intervention or control condition, respectively. Participant costs include time spent completing the eCPP. Resources used will be translated into costs by multiplying the number of units with the cost per unit for each cost category.

Aim 3: RE-AIM data collection. Process tracking forms will be created to record the evaluation data, if not already part of the RCT outcome data (Table 5). These data will be collected monthly by study staff at each site during the recruitment phase from the 4 primary care practice sites, clinicians, and participants.

Table 5. Data and Source for RE-AIM Evaluation

RE-AIM component	Data and Source
REACH: Proportion and characteristics of parents from the practices that were introduced to and enrolled in the study.	# of monthly well-child visits for children aged 2-5 over course of study recruitment (source: EHR) # of parents who were introduced to the study during a well-child visit (source: EHR) # of parents who enrolled in the study (consented/randomized) # of parents who were not introduced to the study and reason (source: EHR) Characteristics of parents enrolled in the study (source: demographics [C.5.a], Technology Inventory ^a)
EFFICACY: Evaluation of intervention efficacy.	Efficacy of the eCPP intervention is assessed as part of the RCT arm of the study by changes in parenting and child behavior. [Specific Aim 1- RCT (Hypothesis 1a)]
ADOPTION: Characteristics of clinicians and practices oriented and agreeing to deliver the intervention (e.g., introduce the study to eligible parents).	Clinician characteristics: MD or NP, specialty, years in practice, and current practices of managing parenting and child behavior concerns (source: Primary Clinician Survey ^b). Site characteristics: # of patients aged 2-5, average time of well-child visits (source: EHR). # of orientation sessions per practice site and proportion of clinicians that attend the orientation (source: attendance records).
IMPLEMENTATION: Assessment of the delivery of the introduction of the study by clinicians and associated costs.	Proportion of clinicians that introduce the study to parents of patients aged 2-5 at well-child visits (source: EHR). Tracking and monitoring any implementation adaptations by the clinicians (source: clinicians). NOTE: Evaluation of implementation-related cost will occur as part of data collection and analysis of Aim 2 [Specific Aim 2- cost-effectiveness analysis] .
MAINTENANCE: Evaluation of the practice site maintenance of implementation procedures and participant level maintenance of behavior change.	Evaluation of maintenance of procedures across the study period at the practice sites (source: recruitment rates, # of parents introduced to the study monthly). # of follow-up orientation sessions for clinicians. Assessment of implementation challenges and facilitators, and sustainability of activities in clinical practice (source: post-implementation interviews with clinicians). Maintenance of behavior change over time will be assessed as part of the RCT arm of the study. [Specific Aim 1- RCT (Hypothesis 1b)]

EHR = Electronic Health Record. ^aThe Technology Inventory includes 18 items for parents to respond to about their use and ownership of technology. ^bThe Primary Clinician Survey⁸⁶ is a 25-item measure developed by Metzler and colleagues for their 2014 NIH-funded grant “Parenting Help Online Study” to assess pediatric primary care clinicians’ current practices in helping parents with child behavior problems and parenting concerns. The measure will be used with permission by the authors; no reliability data has been reported. (Appendix B)

Analytic plan.

Aim 1. Test the direct effects of the 6-module eCPP on parenting outcomes (parenting behavior, self-efficacy, and stress) and child outcomes (child problem and prosocial behavior) compared to an enhanced usual care control condition among low-income parents with young children seen in primary care. **HYPOTHESIS 1A:** Relative to parents in the control condition, parents in the eCPP condition will report greater improvements in parenting and child outcomes at the 3-month assessment. **HYPOTHESIS 1B:** The improvements in parenting outcomes and child outcomes the eCPP condition relative to the control condition will be maintained through the 6- and 12-month assessments.

All analyses for Aim 1 will be performed on an intent-to-treat basis. As multiple dependent variables are being examined, a repeated-measures multivariate analysis of variance (assessment x intervention condition) will be conducted to ensure control of experiment-wise Type-I error, and to perform an initial assessment of intervention effects. We will then test intervention efficacy using multilevel growth models⁹⁰⁻⁹² with three levels (assessments [Level 1] within parent [Level 2] within primary care practice site [Level 3]). Intervention condition will be dummy coded (eCPP vs. control) at Level 2, and covariates at site-level (e.g., clinic size) or parent-level (e.g., age, race/ethnicity) will be included at the appropriate level of analysis. By including baseline measures of the outcome variable being tested as a covariate at Level 2 (parent level) and setting the intercept at the 3-month assessment, we will be able to test Hypothesis 1A (intervention effects between baseline and 3-month assessment) as the main effect of intervention condition (i.e., controlling for baseline level of the outcome being tested). The condition x time interaction will then serve to test differential change in outcome measures following the 3 months of active intervention, and planned contrasts will be estimated to test Hypothesis 1B (maintenance of intervention effects at 6 and 12 months).

Aim 2. Compare the cost-effectiveness of the eCPP intervention relative to control for parenting and child outcomes. **HYPOTHESIS 2:** The eCPP is cost-effective relative to control for parenting and child outcomes.

We will assess cost-effectiveness of eCPP from the societal perspective, including costs borne by the program, health care system, and parent. We will conduct additional analyses from the program, health care system, and parent perspectives separately. For the cost measurement, quantities of resources used and their associated prices will be collected for the eCPP (either prices paid or value of the clinician time) and participant (i.e., value of participant's time to use the eCPP). Program and parent costs will be calculated for the 12-month study duration and summed to calculate total cost per parent. All costs will be valued in 2015 dollars.

For the effectiveness measurement, effectiveness will be measured using the parenting and child outcomes. Cost-effectiveness will be evaluated by combining the mean total cost per parent with effectiveness (parenting and child behavior outcomes). We will calculate the incremental cost-effectiveness ratio (ICER) for eCPP compared to the control condition, such that $ICER = (C_1 - C_0)/(E_1 - E_0)$, where C is cost and E is effectiveness. Subscript 1 denotes eCPP and subscript 0 denotes the control condition; 95% confidence intervals for the ICERs will be calculated to evaluate the uncertainty in these results.⁹³⁻⁹⁵ We will conduct one-way and multi-way sensitivity analyses for the key parameters to evaluate whether the ICERs are sensitive to plausible changes in their values. The sensitivity analysis is a check on the robustness and will determine the key parameters impacting the ICERs. We will also plot acceptability curves based on varying threshold (willingness to pay) values for adherence and change in parenting and child behavior outcomes.

Aim 3. Quantify the levels of program implementation of eCPP in primary care using the RE-AIM framework. **RESEARCH QUESTION 3:** What is the degree of Reach, Efficacy, Adoption, Implementation, and Maintenance of the eCPP intervention in pediatric primary care?

Descriptive statistics will be calculated to identify achievements across each level of RE-AIM for each primary care site. We will develop a demographic, income, and technology use profile for the populations reached (i.e., parents enrolled in the study). We will use contingency table analyses and independent *t* tests to compare the demographic and income profiles to the characteristics of the population of the primary care sites service catchment communities using data from the U.S. Census. This analysis will allow us to assess the extent to which we are either over- or under-representing our priority populations (low-income families) from the local catchment area in this study. Technology ownership and use will be compared to data from national data sets from the Pew Research Center's Internet and American Life Project.⁹⁶

To determine the effectiveness of the implementation strategy and inform dissemination of the eCPP, a cascaded probability model will be constructed.^{97,98} This will be developed based on the following proportions: (a) the likelihood of clinician adoption at the site [*proportion 1 (pr 1)*], (b) the likelihood of implementation (study introduction) by clinicians at the site [*pr 2*], (c) the likelihood of parent enrollment in the study [*pr 3*], and (d) the likelihood of maintenance of behavior change by the eCPP participants [*pr 4*]. *Pr 4* is defined as the proportion of participants whose parenting and child behavior outcomes are the same or improved at the 12-month data collection compared to the 6-month data collection. The estimated likelihood of parents being introduced to the program will be the product of *pr1* and *pr2*. Second, the compound likelihood of parent enrollment in the study will be the product of *pr1*, *pr2*, and *pr3*. Finally, we will estimate the compound likelihood of maintaining behavior change by examining the product of *pr1*, *pr2*, *pr3*, and *pr4*. This analysis will provide us with two important pieces of information: (1) the probable benefits of the program in terms of how likely it is for parents to achieve maintenance of behavior change and (2) inform us of the phase of the implementation process (as operationalized by *pr1*, *pr2*, *pr3*, and *pr4*) which is likely to interfere with the dissemination of the eCPP.

We will conduct a content analysis of the post-implementation interviews with the clinicians. We will use a coding-based system of content obtained from the interviews using the notes taken during the interview using Atlas.ti software. Atlas.ti allows for the identification, organization, and systematizing of codes that can then be assessed in the context of the clinician interviews. Themes will be summarized by site and used to inform the development of processes and procedures to support the implementation and dissemination of the eCPP in pediatric primary care practice sites.

Bibliography & References Cited

1. Children's Defense Fund. Child poverty in America 2013: State analysis. <http://www.childrensdefense.org/zzz-child-research-data-publications/data/child-poverty-in-america-1.pdf>. Updated 2014. Accessed January 12, 2015.

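### Table 4 prices staff time at wage alone, so the costs borne by the program and health care system omit employer-paid benefits

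*Combined protocol and SAP*

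**What the plan says.** Table 4 (Measures, Aim 2: Cost effectiveness analysis) has four rows of staff time, and all are converted to cost at a wage:

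- EHR modification at "Programmer average hourly wage";
- clinicians' time receiving the orientation, and their time introducing the study, both at "Clinician average hourly wage";
- time to lead the orientation at "Study staff average hourly wage".

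The text with Table 4 gives the costing rule: "Resources used will be translated into costs by multiplying the number of units with the cost per unit for each cost category". It adds no later step for benefits, payroll charges or overhead, and no other part of the document mentions them. The same text lists among the resources used for the intervention "modification of the EHR, orientation for clinicians, and time for the clinician to introduce the study to parents during well-child visits".

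The Analytic plan for Aim 2 takes the societal perspective, "including costs borne by the program, health care system, and parent", and adds: "We will conduct additional analyses from the program, health care system, and parent perspectives separately". It describes the price basis for eCPP resources as "either prices paid or value of the clinician time", without saying how that value is set. The ICER is (C1 - C0)/(E1 - E0), with subscript 1 for eCPP and 0 for control.

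**The concern.** The unit price does not measure the cost that the plan says it will count. What a practice or program bears for an hour of a clinician, programmer or staff member is the wage plus the benefits and payroll charges the employer pays. A wage-only price leaves out the second part, and the omission can only lower the unit price.

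Three outputs are exposed. The first is the total cost per parent. The second is the implementation cost, which Table 5 assigns to Aim 2 and which is meant to inform dissemination. The third, under conditions set out in the working, is the ICER with its acceptability curve. The first two are cost levels, so the staff part of each is low wherever staff time is counted. The matter is likely to be most visible in the separate program and health care system analyses, where parent time would not ordinarily dilute it.

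**Working it through.** The documents give no wage, minutes, benefit rate, total cost, ICER or willingness-to-pay threshold, so there is no stated figure to reproduce. The direction can be derived. The size can only be illustrated.

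**Inputs**

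- From the documents: the wage-only unit price (Table 4), cost as units times unit price (text with Table 4), and the ICER formula (Analytic plan, Aim 2).
- Assumed: f, the employer's benefit load as a fraction of wage, 0.2 to 0.4.
- Assumed: s, the share of the wage-priced C1 - C0 that is staff time, 0.05 to 0.5. C1 - C0 is taken to be positive.

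**Step 1: staff cost.** Planned staff cost is W and the cost borne is W(1 + f). The understatement is 1 - 1/(1 + f) = f/(1 + f).

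- f = 0.2: 0.2/1.2 = 16.7%
- f = 0.3: 0.3/1.3 = 23.1%
- f = 0.4: 0.4/1.4 = 28.6%

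**Step 2: incremental total, if the staff rows are charged to eCPP.** The loaded C1 - C0 is the planned one times 1 + sf, so the understatement is sf/(1 + sf).

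| s | f = 0.2 | f = 0.3 | f = 0.4 |
|---|---|---|---|
| 0.05 | 0.01/1.01 = 1.0% | 0.015/1.015 = 1.5% | 0.02/1.02 = 2.0% |
| 0.20 | 0.04/1.04 = 3.8% | 0.06/1.06 = 5.7% | 0.08/1.08 = 7.4% |
| 0.50 | 0.10/1.10 = 9.1% | 0.15/1.15 = 13.0% | 0.20/1.20 = 16.7% |

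With E1 - E0 fixed and positive, the ICER is understated by the same percentages.

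**Step 3: cancellation between arms.** Suppose staff time is 40% of the wage-priced cost before netting, f = 0.3, and a fraction c of staff time is charged equally to both arms. The loaded ICER is then the planned one times [0.6 + 0.4(1 - c)(1.3)] / [0.6 + 0.4(1 - c)].

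- c = 0: (0.6 + 0.52)/1.0 = 1.12
- c = 0.5: (0.6 + 0.26)/0.8 = 1.075
- c = 1: 0.6/0.6 = 1.00

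The factor falls to 1 when everything is shared, and never below it.

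**The case against.** A reader might infer that wage-only pricing necessarily favours Hypothesis 2. The documents do not support that. Randomization is within sites at the participant level (Study Design), so the same practices, oriented clinicians and modified EHR serve both arms. The Table 4 footnote spreads introduction time for all parents over the participants without naming an arm. If that average is charged to everyone, it drops out of C1 - C0. The text with Table 4 does list EHR modification, orientation and introduction time as resources of the intervention, which points to eCPP, but the plan does not settle the allocation. The ICER statement also needs E1 > E0, and no fixed threshold is given against which a changed decision could be shown.

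A reader might also infer that the health care system total is short by the whole benefit load. No Table 4 row is assigned to a perspective. Study-staff and programmer time might be program cost, and invoiced tablet and support costs might fall to the health care system and dilute the effect. Even a total made up only of staff time would be short by f/(1 + f), not by f.

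Nor does the net direction of staff cost as built follow from the unit price. If the introduction row is charged to eCPP, it includes time with parents who never enrol, which pushes eCPP cost up. That is a question of which minutes are counted. It does not offset a low price per minute by any known amount.

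Two mitigating readings carry less weight. The phrase "either prices paid or value of the clinician time" could admit a loaded rate, and the wage labels are never defined. But Table 4 is the only operational definition, so a clarification is needed even if a loaded rate was meant. The planned one-way and multi-way sensitivity analyses could vary unit prices, but the parameters are not named, and varying a price around a wage-only base case leaves the headline ICER and its interval unloaded.

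**Conclusion.** The point stands as a minor costing defect in a secondary aim. Followed literally, Table 4 prices staff time below what the program and health care system bear. This understates the staff part of the cost per parent and of the implementation cost.

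For the ICER the conclusion is conditional: it is too low to the extent that the staff rows are charged to eCPP and E1 > E0. It is unaffected by any part shared equally between arms, and this pricing choice does not bias it the other way.

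The illustrated size is 17-29% of staff cost. For the incremental total it runs from about 1-2% at a 5% staff share to 9-17% at a 50% share. These figures rest entirely on the assumed 20-40% load and the assumed staff shares, and on reading wage in its ordinary sense, without benefits. A change in the conclusion on Hypothesis 2 cannot be shown from the documents.

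**What to change.** - In the four staff rows of Table 4, replace hourly wage with average hourly compensation, defined as wage plus employer-paid benefits, in the base case for programmer, clinician and study-staff minutes.
- State for each staff row which arm carries it and which perspective (program or health care system) it enters.
- Name the benefit rate as a one-way sensitivity parameter, with its range.

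The parent-time rows are outside this change, because the text with Table 4 treats them as opportunity cost rather than an employer's outlay. One sentence saying so would keep the valuation basis clear.

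The cost is a few words in Table 4 and one benefit rate obtained from each employer, with no further data from participants. The downside is that the reported cost per parent, and possibly the ICER, becomes slightly less favourable to eCPP.

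### The Aim 1 MANOVA is said to ensure experiment-wise Type I error control, but the per-outcome growth-model tests that decide Hypotheses 1A and 1B would be only weakly protected even if they were conditional on it

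*Combined protocol and SAP*

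**What the plan says.** Under *Measures, Outcome variables*, the combined protocol and SAP names five primary constructs: "Primary parenting outcome variables include parenting behavior, self-efficacy, and stress", and "The primary child outcomes are child behavior problems and prosocial behavior". Six instruments measure them. Parenting behavior alone has two, the PQ and the PARYC. The text does not say which scores are analysed.

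Under *Analytic plan, Aim 1*, the plan notes that there are several dependent variables and that for this reason "a repeated-measures multivariate analysis of variance (assessment x intervention condition) will be conducted to ensure control of experiment-wise Type-I error". The MANOVA is also to give a first look at the effects. The next sentence begins "We will then test intervention efficacy using multilevel growth models". These models are fitted one outcome at a time, as the covariate shows: "By including baseline measures of the outcome variable being tested as a covariate at Level 2 (parent level". The condition effect at 3 months tests Hypothesis 1A. After that, "The condition x time interaction will then serve to test differential change in outcome measures following the 3 months of active intervention", and planned contrasts at 6 and 12 months test Hypothesis 1B.

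For the growth-model tests, the supplied text gives no significance level, adjusted threshold, hierarchy or statement that they depend on the MANOVA result.

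**The concern.** The plan assigns experiment-wise error control to one test and decides its hypotheses with others. The only link is the word *then*, which gives an order and not a condition. If the growth models are run whatever the MANOVA shows, the MANOVA cannot affect their error rate. If they are run only after a significant MANOVA, one real effect is enough to open the way to unadjusted tests of every other outcome.

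The results will be read outcome by outcome: which parenting or child outcomes improved, and which improvements lasted. A reader who trusts the stated property would take each significant outcome as protected at the experiment-wise level. In a mixed result, with some outcomes improving and two or more not, that protection is absent.

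**Working it through.** **No figure to reproduce.** The documents give no alpha, family-wise error rate or power for Aim 1. The figures below are therefore illustrations.

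**Inputs from the documents.** 312 parents, 156 per arm; four assessments (baseline, 3, 6 and 12 months); five primary constructs. The scales number PQ 3 + PARYC 3 + PSOC 2 + PSI-SF 3 + ECBI 2 + SDQ 5 = 18.

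**Assumed.** Two-sided alpha 0.05; equal between-scale correlation 0.3–0.7; between-visit correlation 0.4–0.6; complete data; effects kept to 12 months. Family sizes of 5 (one score per construct) and 18 (every scale) are examples.

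**Step 1: no precondition, nothing works.** For m independent tests the chance of at least one false positive is 1 − 0.95^m. This is 0.226 for m = 5 and 0.603 for m = 18. Correlation lowers it, to 14–21% and 28–53% in the simulation of step 3.

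**Step 2: precondition, by reasoning.** If no outcome is affected, a false positive requires the MANOVA to reject, so the rate cannot exceed its alpha. If some outcome is affected strongly enough that the MANOVA nearly always rejects, the m0 null outcomes are in effect tested unadjusted. For independent tests the rate then approaches 1 − 0.95^m0:
- m0 = 1: 0.050, no inflation
- m0 = 2: 0.098
- m0 = 4: 0.185
- m0 = 17: 0.582

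If every outcome is affected, m0 = 0 and no false positive is possible. Inflation therefore needs at least one affected outcome and at least two null ones.

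**Step 3: precondition in the planned form.** The MANOVA was simulated as a Hotelling T² test on the three change-from-baseline contrasts of all scores (assessment by condition). Each score then had a 3-month between-arm test adjusted for its own baseline. There were 4,000 replicates for 5 scores and 2,500 for 18. The row for two or three true effects used 1,500 replicates, d = 0.3–0.4, between-scale correlation 0.3 or 0.7 and between-visit correlation 0.4.

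| Chance of at least one false-positive 3-month outcome | 5 scores | 18 scores |
|---|---|---|
| Precondition, no true effect | 0.013–0.025 | 0.023–0.040 |
| Precondition, one true effect, d = 0.3–0.5 | 0.110–0.177 | 0.149–0.473 |
| Precondition, two or three true effects | about 0.07–0.14 | not run |
| No precondition, no true effect | 0.139–0.209 | 0.283–0.528 |

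The Monte Carlo standard error is about √(0.15 × 0.85 / 4,000) = 0.006 for 5 scores and √(0.4 × 0.6 / 2,500) = 0.010 for 18.

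**Step 4: role of correlation.** It does not act in one direction. With 18 scores and one effect of d = 0.3, the conditional rate is about 15% at correlation 0.3 and 19% at 0.7, because higher correlation makes the MANOVA more likely to reject. At d = 0.5 the largest rates occur at lower correlation.

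**Step 5: 6 and 12 months.** No rate is given, because the text does not say whether the Hypothesis 1B contrasts compare the arms at each visit.

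**The case against.** Four points can be made for the plan.

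- **Missing text.** References 87–89 (a trial-reporting statement, multiple imputation, exploratory data analysis) are listed but not cited in the supplied text. By citation order, their text would fall between the Table 5 footnote and the growth-model sentence. An alpha, a list of scores or an adjustment rule could have stood there. This stands. A reader might infer that the plan has no multiplicity rule at all; the documents show only that none is in the supplied text. The absence of alpha and of a score list is likewise not claimed as a defect. A missing statement that made the MANOVA a precondition would not be enough, because control would still be weak.
- **Intent.** A stated purpose of error control, followed by *then*, most naturally means a precondition. This also stands. The 14–21% and 28–53% figures belong to the less natural reading, and with a precondition and no effects the rate is only 1–4%.
- **Extreme case.** The 15–47% range needs all 18 scales tested, exactly one affected and 17 exactly null. The plan does not say that 18 are analysed; totals are mentioned for the PSOC and PSI-SF. A reader might take 47% as the error rate of this trial, and the documents do not support that. It is an upper example.
- **Hypothesis 1A predicts improvement throughout.** If that is right, no false positive is possible. But error control is needed for the case where the prediction is only partly right.

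A MANOVA before univariate tests is common practice, but that does not turn weak control into strong control.

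**Conclusion.** The concern holds. The plan claims a property that its stated design does not have. On the more natural reading, control is lost once at least one outcome is affected and two or more are null. That conclusion follows from the structure of the tests and does not rest on the assumed figures.

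The size is illustrative and covers 3 months only. With 5 scores it is moderate, about 11–18% with one true effect and 7–14% with two or three, against an assumed 5%. With 18 scores and one true effect it could reach 15–47%.

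The point should be fixed, but it does not undermine the growth models as estimates of effect. Confidence is high that the stated control is not delivered by the MANOVA, and lower on whether a separate adjustment existed in text not supplied.

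**What to change.** If an adjustment rule exists elsewhere, cite it. If not, replace the claim of experiment-wise control with one of these:

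- (a) *The MANOVA is an initial global test. Growth-model p-values for individual outcomes are not adjusted for multiplicity.*
- (b) *Growth models are interpreted only if the MANOVA is significant. This controls experiment-wise error only when no outcome is affected.*

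Either costs wording only.

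If experiment-wise control is to be kept:

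1. State alpha and name one primary score per construct, which means choosing between the PQ and the PARYC for parenting behavior.
2. Apply Holm to the 3-month between-arm tests (Hypothesis 1A).
3. Define the 6- and 12-month contrasts as between-arm comparisons. Test them only for outcomes that pass Hypothesis 1A, and count them in the procedure so that strong control holds over the whole set.
4. Do not apply Holm to a condition × time test whose non-significance would be read as maintenance. A stricter threshold would make fading harder to detect and so favour Hypothesis 1B. Report that test with its confidence interval.

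The cost of Holm is power. Before baseline adjustment, the effect detectable with 80% power is d = (z₁₋₀.₀₂₅/ₖ + 0.842) × √(2/n). At n = 156 per arm, one test gives (1.960 + 0.842) × 0.1132 = 0.32. The first Holm step over 5 tests gives (2.576 + 0.842) × 0.1132 = 0.39. With an assumed 20% dropout (125 per arm), the rise is from 0.35 to 0.43.
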